12.3 Sample Size and Accrual

It is assumed that LAPC patients have a DCR of 45% with standard of care, whereas LAPC patients will have DCR rate of 75% under the protocol in this study. A minimax Simon's two-stage design will be implemented with 12 patients evaluated in the first stage. If 5 or fewer responses are observed from these 12 patients, then the study will be stopped for futility. Otherwise, an additional 13 patients will be added yielding a total sample size of 25 patients. The study will be considered successful if 16 or more responses are observed in the 25 patients. This design comprises a type 1 error rate of 5% and a power of 80% when the true DCR is 75%.

Therefore, this study seeks to recruit 12 to 25 patients depending on results of the first stage evaluation. Assuming approximately 10% of the patients would not be evaluable, the target sample size is 28 patients.

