12.6 Data Analysis Plans

12.6.1 Analysis Plans for Primary Objective

The primary endpoint for this study is disease control rate (DCR).

In the study by Loehrer *et al.*, 37 patients with LAPC treated with gemcitabine alone reported an objective response rate (ORR) of 5% and stable disease rate (SDR) of 35%, hence a DCR of 40%. As reported by Lakatos *et al.*, 32 patients with LAPC were treated with a modified FOLFIRNOX protocol reported an ORR (partial regression only) of 18.8% and SDR of 56.2%, hence a DCR of 75%. For determining the sample size for this one-arm clinical trial, we will consider the study successful if the DCR is statistically significant from 45%.

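### The stated 80% power at a DCR of 75% does not follow from the 16-of-25 rule (exact power 92.5%), and section 12.6.1 does not tie its significance criterion to that rule

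*Combined protocol and SAP*

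**What the plan says.** Section 12.3 (Sample Size and Accrual), repeated in the synopsis, gives the hypotheses: "It is assumed that LAPC patients have a DCR of 45% with standard of care", and "LAPC patients will have DCR rate of 75% under the protocol in this study". It then gives the design: "A minimax Simon's two-stage design will be implemented with 12 patients evaluated in the first stage". The interim rule is "If 5 or fewer responses are observed from these 12 patients, then the study will be stopped for futility". If that bound is passed, a second stage of 13 brings the total to 25. The final rule is "The study will be considered successful if 16 or more responses are observed in the 25 patients". The claimed operating characteristics are "This design comprises a type 1 error rate of 5% and a power of 80% when the true DCR is 75" per cent.

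Section 12.6.1 (Analysis Plans for Primary Objective) cites the two historical series and then says "we will consider the study successful if the DCR is statistically significant from 45" per cent. That sentence opens by giving its purpose as setting the sample size. The section names no test, significance level or direction, and it does not mention the boundary of 16. Neither section says whether the 5% is one-sided or two-sided.

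**The concern.** Section 12.3 fixes the sample size, both boundaries and both hypotheses, so its type I error and power can be computed exactly. If the printed power does not follow from the printed rule, then the power, the alternative or the boundary is not what the designers intended. A reader cannot then tell which effect the trial was sized to detect.

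Section 12.6.1 is the only analysis text for the primary objective, and it expresses success as significance rather than as a count. If that does not lead to the same cut-off as section 12.3, a result of exactly 16 of 25 leaves room to choose the test after the data are seen.

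**Working it through.** **Inputs (section 12.3):** p0 = 0.45, p1 = 0.75, n1 = 12, stop if 5 or fewer, second stage 13, N = 25, success if 16 or more.

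**Formula.** With X1 ~ Bin(12, p) and X2 ~ Bin(13, p):

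P(success | p) = Σ over x = 6 to 12 of P(X1 = x) × P(X2 ≥ 16 − x)

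**1. The plan's own figures.** Each column gives the contribution of one first-stage count.

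| x | p = 0.45 | p = 0.70 | p = 0.75 |
|---|---|---|---|
| 6 | 0.0043 | 0.0333 | 0.0235 |
| 7 | 0.0104 | 0.1037 | 0.0820 |
| 8 | 0.0136 | 0.1929 | 0.1781 |
| 9 | 0.0099 | 0.2248 | 0.2518 |
| 10 | 0.0039 | 0.1647 | 0.2310 |
| 11 | 0.0008 | 0.0709 | 0.1266 |
| 12 | 0.0001 | 0.0138 | 0.0317 |
| **Sum (before rounding)** | **0.0429** | **0.8042** | **0.9245** |

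- Type I error at 45% is 4.3%. It reproduces the stated 5% as an upper limit, which is how a discrete design is normally quoted.
- Power at 75% is 92.5%. The stated 80% does not reproduce.
- The futility stop does not explain the gap. With no interim look, 16 of 25 would have power 92.9% at 75%, so the stop costs about 0.4 percentage points.

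**2. Where 80% would come from.** Power is 80.4% at a true DCR of 70%. An exhaustive search for the Simon minimax design with error at most 5% and power at least 80% gives:

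- 45% versus 70%: n1 = 12, stop at 5 or fewer, N = 25, success at 16 or more. This is exactly the design in section 12.3.
- 45% versus 75%: n1 = 6, stop at 2 or fewer, N = 16, success at 11 or more (error 4.7%, power 80.2%).

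So the printed design is the minimax design for an alternative of 70%, and is not the minimax design for the printed alternative of 75%.

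**3. Significance against 45%, at 25 evaluable patients (section 12.6.1).**

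| Count | One-sided exact p | Two-sided exact p | 95% exact CI |
|---|---|---|---|
| 15/25 | 0.096 | 0.160 | 38.7–78.9% |
| 16/25 | 0.044 | 0.070 | 42.5–82.0% |
| 17/25 | 0.017 | 0.026 | 46.5–85.1% |

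- One-sided at 5%, the smallest significant count is 16, the same as section 12.3.
- Two-sided at 5%, the smallest is 17. With the futility stop, a cut-off of 17 has one-sided error 1.7% and power 84.9% at 75%, so the stated 80% does not fit that rule either.
- With the futility stop, the chance of landing exactly on 16 is the difference between the two cut-offs: 92.45% − 84.91% ≈ 7.5% at a true DCR of 75%, and 80.42% − 67.50% ≈ 12.9% at 70%.
- The two-sided 90% exact interval at 16/25 is 45.6–79.8%. It excludes 45%, in agreement with the one-sided 5% test.

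**The case against.** The power error is on the safe side. If the true DCR is 75%, the trial has more power than it claims, so nothing is lost in its ability to detect that effect. This stands, and it limits the consequence, but the printed figure is still wrong.

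A reader might infer that the plan contains two conflicting success criteria, with 16 of 25 a success in section 12.3 and a failure in section 12.6.1. The documents do not support this. The sentence in 12.6.1 is introduced as a sample-size statement, and no section adopts a two-sided test or makes a 95% interval the decision rule. The trial has one arm, a futility-only interim and a success rule in one direction, and Simon designs are conventionally one-sided. On that reading 16 is exactly the smallest significant count at 25 evaluable patients, so the two sections agree. A 95% interval that includes 45% alongside a significant one-sided 5% test is then an ordinary reporting mismatch. What remains is that sidedness is never stated and 12.6.1 does not cite the boundary.

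A reader might also infer that both stated error rates are wrong. The type I error is not: 4.3% meets the 5% limit. Only the power fails.

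Finally, it is tempting to conclude that 75% is a misprint for 70%. The exact match with the minimax design makes that plausible, but 70% appears nowhere in the documents and one of the cited series has a DCR of 75%. It stays an inference for the sponsor to confirm or reject.

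**Conclusion.** The power statement in section 12.3 and the synopsis is wrong as written: the rule has 92.5% power at a true DCR of 75%, about 12.5 percentage points above the stated 80%. The attained one-sided type I error of 4.3% is consistent with the stated 5%. This result uses only the design parameters printed in section 12.3. It assumes independent binomial outcomes, a binding futility stop and exactly 25 evaluable patients, and it does not depend on sidedness.

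The wording of section 12.6.1 is a secondary point, an ambiguity and not a proven contradiction. It would change the conclusion only at exactly 16 of 25, and only if someone applied a two-sided test that the plan never specifies.

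**What to change.** - **Section 12.3 and synopsis:** reconcile the power and the alternative. State either 92.5% power at a DCR of 75% or, if 70% was the intended alternative, 80.4% power at 70%. The sponsor should check the original design calculation to decide which. Give the attained one-sided type I error of 4.3%.
- **Section 12.6.1:** replace the significance sentence with a reference to the 12.3 rule (16 or more of 25, one-sided test against 45%) as the sole success criterion.
- **Reporting:** give the DCR with a two-sided 90% exact interval (45.6–79.8% at 16/25), so that the interval agrees with the one-sided 5% test. Note that this interval ignores the futility stage.

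The cost is wording only, with no change to patient numbers or boundaries. The one drawback is that the test must be openly labelled as one-sided. The change should be made before the primary results are known.

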12.6.2 Analysis Plans for Secondary Objectives

The Secondary Objectives will be analyzed as described in the section 12.2.2, Definition of Secondary Endpoints.

12.7 Interim Analysis/Criteria for Stopping Study

A single interim analysis for futility will take place when the 12th subject has completed 6 months of follow-up. The proportion of subjects that is tumor progression-free at 6 months will be assessed along with other efficacy and safety data in making the determination if the study should continue. If 5 or fewer responses are observed from these 12 patients, then the study will be stopped for futility. Otherwise, an additional 13 patients will be added yielding a total sample size of 25 patients. Accrual will continue during the interim analysis. Recruitment will be halted if futility is determined.

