12.5 Assessment of Efficacy

This will comprise all subjects who receive at least one dose of trial drug and either undergo at least one post-baseline assessment or die before any evaluation.

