13.2 Penn State Cancer Institute Internal Data Safety Monitoring Board

The PSCI DSMB will review the following on a semi-annual basis:

- Adverse event summary report
- Audit results, if applicable
- Data related to stopping/decision rules described in study design

- Study accrual patterns
- Protocol deviations

Documentation of these reviews will be provided to sponsor-investigator and Big Ten CRC AHQ. Issues of immediate concern by the PSCI Internal DSMB will be brought to the attention of the sponsor-investigator and other regulatory bodies as appropriate. The sponsor-investigator will work with Big Ten CRC AHQ to address the concerns.

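### The stated recruitment range of 12 to 25 does not match a futility look held 6 months after the 12th subject with accrual open; about 20 to 23 would be enrolled at a stop

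*Combined protocol and SAP*

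**What the plan says.** Section 12.3 sets a Simon two-stage design with "12 patients evaluated in the first stage". The trial stops for futility at 5 or fewer responses. Otherwise 13 more patients are added, and 16 or more responses in 25 is a success. The section then says that "this study seeks to recruit 12 to 25 patients depending on results of the first stage evaluation", and next: "Assuming approximately 10% of the patients would not be evaluable, the target sample size is 28 patients". The synopsis (Statistical Considerations) repeats this and gives an estimated enrolment period of 18 months.

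Section 12.7 fixes the timing: "A single interim analysis for futility will take place when the 12th subject has completed 6 months of follow-up". It adds "Accrual will continue during the interim analysis" and halts recruitment only if futility is determined. At that look, 6-month progression-free status "will be assessed along with other efficacy and safety data in making the determination if the study should continue".

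Two further places bear on the point. Section 12.5 counts for efficacy those dosed subjects who "either undergo at least one post-baseline assessment or die before any evaluation". Section 13.2 has the data safety monitoring board (DSMB) review, twice a year, "Data related to stopping/decision rules described in study design". Tumour imaging is scheduled every 4 cycles, that is every 8 weeks (section 7, footnote 7).

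**The concern.** A reader of 12.3 or the synopsis takes the smallest trial to be 12 patients: stage 1 fails and nobody else is enrolled. Under 12.7, enrolment runs through the whole 6 months after the 12th subject, so a good part of the stage 2 group is already on treatment when the futility decision is made. The stated range understates how many people a trial that stops for futility will enrol.

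A second, smaller matter follows. The stage 1 rule is lost as soon as 7 of the 12 cannot be successes, because at most 5 responses are then possible. That can be known before the planned look, yet 12.7 names only the 6-month time point and no text tells anyone to act sooner.

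**Working it through.** **Inputs from the documents.** DCR 45% (standard of care) and 75% (target); stage 1 of 12 with a stop at 5 or fewer; 25 in total with success at 16 or more; 10% not evaluable; target 28; enrolment period 18 months; look 6 months after the 12th subject.

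**The plan's own figures.** 25/(1 − 0.10) = 27.8, rounded up to 28, which reproduces. The exact probability of declaring success (more than 5 of 12, then at least 16 of 25) is 0.043 at 45%, within the stated 5%. At 75% it is 0.925, not the stated 80%; that is a different issue and nothing here depends on it. The probability of a futility stop, P(X ≤ 5 | 12, p), is 0.527 at 45%, 0.158 at 60% and 0.014 at 75%.

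**Enrolled at the look.** Assumption: uniform accrual of N subjects over D months. Enrolled = min(N, 12 + 6 × N/D).

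| D (months) | N = 25 | N = 28 |
|---|---|---|
| 12 | 24.5 | 26.0 |
| 18 | 12 + 6 × 25/18 = 20.3 | 12 + 6 × 28/18 = 21.3 |
| 24 | 18.2 | 19.0 |
| 36 | 16.2 | 16.7 |

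At 18 months, a stop at the look spares 25 − 20.3 = 4.7 of the 13 stage 2 subjects, or 28 − 21.3 = 6.7 of the 16 planned after the 12th.

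If stage 1 needs 12 evaluable subjects, 12/0.9 = 13.3 must be enrolled first. The count at 18 months becomes 13.3 + 8.3 = 21.7 (N = 25) or 13.3 + 9.3 = 22.7 (N = 28). Reading 6 months as 24 weeks (5.52 months) lowers the figures for the first 12 enrolled only to 19.7 and 20.6.

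**Gain from acting at the 7th certain failure.** This was simulated with uniform 18-month accrual, the first 12 enrolled, a 24-week endpoint and failures found at the week 8, 16 and 24 scans. Whole subjects were counted, for N = 25 and N = 28. The timing of failures is assumed, since the documents give none. The favourable case has equal conditional risk at each scan and no reporting lag. The unfavourable case has 10/30/60% of failures at the three scans and a 1-month lag.

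| True DCR | Fewer enrolled, in expectation |
|---|---|
| 45% | 1.0 to 3.0 |
| 60% | 0.2 to 0.8 |
| 75% | under 0.1 |

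At 45%, when a futility stop occurs, the decision comes 1.3 to 3.6 months earlier with 2.0 to 5.7 fewer enrolled. The rejection probabilities stay at 0.043 and 0.925, because the trigger only recognises a stage 1 result that is already determined.

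**The case against.** The strongest reply is that nobody is really misled. Section 12.3 speaks of patients evaluated in stage 1 and gives a target of 28 straight after the 12-to-25 sentence, so the range cannot be a literal enrolment range. Section 12.7 states openly that accrual continues. Much of this stands: it makes the point minor, but it does not make the sentence right. The target of 28 corrects the upper end of the range, and nothing corrects the lower end. The accrual sentence in 12.7 could be read as covering only the days of the analysis itself, but even then no text closes enrolment during the 6-month wait.

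On the early trigger, the reply is that a stage 1 rule applied once the data are complete is valid, that nothing promises earlier stopping, and that the DSMB sees the relevant data twice a year and can raise urgent issues. That stands too. The missing trigger is an opportunity, not an error.

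Three stronger readings are tempting, and the documents do not support them:

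- A reader might infer that open accrual damages the design. It does not: the first 12 decide stage 1, and type I error and power are unchanged.
- A reader might infer that 12 and 25 are wrong sample sizes. They are sound as evaluable numbers.
- A reader might infer that the extra subjects are harmed. The 45% behind the largest gain is the rate that 12.3 assumes for standard of care, and the documents give no evidence that these subjects would do worse.

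**Conclusion.** The recruitment sentence in 12.3 and the synopsis is wrong as written, in a minor way. Under 12.7, about 20 to 23 subjects rather than 12 would be enrolled at a futility stop. The figure rests on uniform accrual over the estimated 18 months and on whether the 12 are enrolled or evaluable subjects. The conclusion that it exceeds 12 does not depend on the exact period, since even 36 months gives 16 to 17 for the first 12 enrolled. At a true DCR of 45%, a stop has probability 0.527, so this is not a remote case.

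The early trigger is a cheap, optional improvement. Its benefit is modest and shrinks quickly as the true DCR rises above 45%. The gain was simulated for the first 12 enrolled, not for the first 12 evaluable subjects that the suggested rule would use, and it did not model resected subjects or missing 24-week scans.

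**What to change.** **Change 1 (correction).** In 12.3 and the synopsis, describe 12 and 25 as the evaluable numbers for the stage 1 and final analyses. State enrolment separately, for example: *Because accrual continues, about 20 to 23 subjects are expected to be enrolled at a futility stop (uniform accrual over 18 months), against a target of 28.* The cost is one sentence. No accrual pause is needed.

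**Change 2 (optional).** Add to 12.7: *The stage 1 futility boundary is met once 7 of the first 12 evaluable subjects can no longer count as successes under the primary endpoint definition; the futility determination is then made without waiting for the 6-month look.* The cost is a running count from scans already scheduled, and a determination made with less mature data on the other efficacy and safety items. Where section 9.6 requires later confirmation of non-target progression, no deadline is given, so the count should say whether it waits for that confirmation.

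Change 2 cannot operate until one endpoint definition is settled. Sections 12.2.1 (24 weeks), 9.8.4 (stable disease for 8 weeks) and 2.2.1 (subjects remaining unresectable) differ. That is a separate matter, which the primary analysis needs resolved anyway, and it adds no weight to this point.

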13. TRIAL MANAGEMENT

13.1 Data and Safety Monitoring Plan (DSMP)

The study will be conducted with guidance with the Penn State Cancer Institute's (PSCI) DSMP.

Big Ten CRC AHQ oversight activities include:

- Review and process all adverse events requiring expedited reporting as defined in the protocol
- Notify participating sites of adverse events requiring expedited reporting
- Provide trial accrual progress, safety information, and data summary reports to the sponsor-investigator
- Submit data summary reports to the PSCI Internal Data Safety Monitoring Board for review as per their DSMP
- Submit data summary reports to the DSMB for review according to the site DSMP

13.2 Penn State Cancer Institute Internal Data Safety Monitoring Board

The PSCI DSMB will review the following on a semi-annual basis:

- Adverse event summary report
- Audit results, if applicable
- Data related to stopping/decision rules described in study design

- Study accrual patterns
- Protocol deviations

Documentation of these reviews will be provided to sponsor-investigator and Big Ten CRC AHQ. Issues of immediate concern by the PSCI Internal DSMB will be brought to the attention of the sponsor-investigator and other regulatory bodies as appropriate. The sponsor-investigator will work with Big Ten CRC AHQ to address the concerns.

13.3 Data Quality Oversight Activities

Remote validation of the EDC system data will be completed on a continual basis throughout the life cycle of the study. Automated edit check listings will be used to generate queries in the EDC system and transmitted to the site to address in a timely fashion. Corrections will be made by the study site personnel.

Monitoring visits to the trial sites may be made periodically during the trial to ensure key aspects of the protocol are followed. Additional for-cause visits may occur as necessary. Source documents will be reviewed for verification of agreement with data entered into the EDC system. It is important for the site investigator and their relevant personnel to be available for a sufficient amount of time during the monitoring visits or audit, if applicable. The site investigator and institution guarantee access to source documents by Big Ten CRC AHQ or its designee.

The trial site may also be subject to quality assurance audit by Ipsen Biopharmaceuticals or its designee as well as inspection by appropriate regulatory agencies.

13.4 Compliance with Trial Registration and Results Posting Requirements

Under the terms of the Food and Drug Administration Modernization Act (FDAMA) and the Food and Drug Administration Amendments Act (FDAAA), the sponsor-investigator of the trial is solely responsible for determining whether the trial and its results are subject to the requirements for submission to the Clinical Trials Data Bank, http://www.clinicaltrials.gov. All results of primary and secondary objectives must be posted to CT.gov within a year of completion. The sponsor-investigator has delegated responsibility to Big Ten CRC AHQ for registering the trial and posting the results on clinicaltrials.gov. Information posted will allow subjects to identify potentially appropriate trials for their disease conditions and pursue participation by calling a central contact number for further information on appropriate trial locations and study site contact information.

14. DATA HANDLING AND RECORD KEEPING

14.1 Data Management

Big Ten CRC AHQ will serve as the Clinical Research Organization for this trial. Data will be collected through a web-based clinical research platform compliant with Good Clinical Practices and Federal Rules and Regulations. Big Ten CRC AHQ personnel will coordinate and manage data for quality control assurance and integrity. All data will be collected and entered into the EDC system by study site personnel from participating institutions.

14.2 Case Report Forms and Submission

Generally, clinical data will be electronically captured in the EDC system and correlative results will be captured in the EDC system or other secure database(s). If procedures on the study calendar are performed for standard of care, at minimum, that data will be captured in the source document. Select standard of care data will also be captured in the EDC system, according to study-specific objectives. Please see the Data and Safety Oversight Process (DSOP) guidelines for further details.

The completed dataset is housed at Big Ten CRC AHQ and is the sole property of the sponsorinvestigator's institution. It should not be made available in any form to third parties, except for authorized representatives of appropriate Health/Regulatory Authorities, without written permission from the sponsor-investigator and Big Ten CRC AHQ. After the initial publication, the complete data set will be available to all Big Ten CRC institutions.

